7.8 Standard Calculations

7.8.1 Age

Age will be calculated according to the formula noted below.

$$\text{Age (years)} = \text{integer of } [(\text{date of informed consent} - \text{date of birth}) / 365.25]$$

7.8.2 Body Mass Index (BMI)

BMI will be calculated using height (in cm) and weight (in kg) according to the formula noted below.

$$\text{BMI (kg/m}^2\text{)} = \text{Weight (kg)} / [\text{Height (cm)} / 100]^2$$

7.8.3 Change from baseline

Change from baseline will be calculated for each post baseline visit as follows:

$$\text{Change From Baseline} = \text{Post baseline result at time} - \text{Baseline result}$$

7.8.4 Time to event

Time to event will be calculated according to the formula noted below:

$$\text{Time to event} = (\text{Date of Event} - \text{Date of study treatment initiation}) + 1$$

[REDACTED]

[REDACTED]

[REDACTED]

[REDACTED]

[REDACTED]

[REDACTED]

[REDACTED]

[REDACTED]

[REDACTED]

[REDACTED]

[REDACTED]

[REDACTED]

[REDACTED]

[REDACTED]

[REDACTED]

[REDACTED]

[illegible]

All statistical analyses will be performed using SAS® for Windows, version 9.4 or later, and Phoenix® 8.1 WinNonlin® version or higher (Certara USA, Inc., Princeton, USA). All data collected during this study will be presented in subject data listings.

[REDACTED]

8.1 Summarizing Disposition and Baseline Data

8.1.1 Subject Disposition and Withdrawals

There will be a detailed accounting of all subjects who sign an informed consent to participate in this trial. [REDACTED]

- [REDACTED]
- [REDACTED]
- [REDACTED]
- [REDACTED]
- [REDACTED]
- [REDACTED]
- [REDACTED]
- [REDACTED]

[REDACTED]

8.1.2 Protocol Deviations

Protocol deviations for all enrolled subjects will be listed as by-subject listing and summarized descriptively.

8.1.3 Demographics and Baseline Characteristics

[REDACTED]

8.1.4 Medical History

Medical history will be coded using the most current available version of Medical Dictionary for Regulatory Activities (MedDRA) and will be summarized by system organ class (SOC) and preferred term (PT). Medical history results will be provided as by-subject listings and summarized.

8.1.5 Prior and Concomitant Medications

Prior medication is defined as any medications with an end date prior to the first treatment date.

All prior and concomitant medications recorded in the case report form will be listed and coded to matching Anatomic Therapeutic Classification codes using the most recent version of WHO Drug dictionary, and summarized by cohort and by the number and percentage of subjects taking each medication for the Safety population.

8.1.6 Prior Anti-Cancer Treatments

All prior anti-cancer treatments (i.e., Radiotherapy, Chemotherapy/Immunotherapy, and Surgery) recorded in the case report form will be presented as by-subject listings.

8.1.7 Extent of Exposure and Treatment Compliance

All treatment administration data will be listed and summarized for the Safety population by cohort.

[REDACTED]

[REDACTED]

[REDACTED]

[REDACTED]

[REDACTED]

[REDACTED]

[REDACTED]

[REDACTED]

[REDACTED]

[REDACTED]

[REDACTED]

[REDACTED]

[REDACTED]

[REDACTED]

[REDACTED]

[REDACTED]

[REDACTED]

[REDACTED]

[REDACTED]

[REDACTED]

[REDACTED]

[REDACTED]

[REDACTED]

[REDACTED]

[REDACTED]

[REDACTED]

[REDACTED]

[REDACTED]

[REDACTED]

[REDACTED]

8.2 Analysis of Efficacy Data

[REDACTED]

8.2.1 Primary Outcome Measure

The primary efficacy outcome measure for part 1 is determination of the MTD of 2X-121 monotherapy.

The primary efficacy outcome measure for part 2 is determination of the MTD of dovitinib given in combination with 2X-121 monotherapy.

8.2.1.1 Maximum Tolerated Dose (MTD)

The MTD is defined as the highest dose that does not produce unacceptable toxicity, or 1 dose level below the dose in which dose limiting toxicities (DLTs) were observed in \geq 33% of the participants during the first 14 days of the main treatment period.

MTD will be determined by sponsor in consultation with the safety assessment committee.

8.2.1.2 Dose Limiting Toxicity (DLT)

All toxicities will be graded using NCI-CTCAE Version 5.0.

All DLTs will be presented as a by-subject listing and summarize descriptively for both parts of the study.

8.2.3 Exploratory Outcome Measures

[illegible]

8.3 Analysis of Safety Data

All safety analyses will be conducted using the Safety population. All data collected will be summarized according to the variable type. No inferential statistics are planned.

8.3.1 Adverse Events

Adverse events will be classified by system organ class (SOC) and preferred term (PT) according to the most recent version of MedDRA dictionary.

TEAE are defined as adverse events with onset date on or after the first treatment. TEAEs will be summarized by treatment group, System Organ Class, and preferred term. [REDACTED]

[REDACTED]

[REDACTED]

[REDACTED]

[REDACTED]

[REDACTED]

[REDACTED]

[REDACTED]

[REDACTED]

[REDACTED]

[REDACTED]

[REDACTED]

All adverse events recorded in the eCRF will be presented as by-subject listings.

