4.4.2. Follow Up Visit (FU)

Follow-up visits will be done for survival status, by clinic visits or phone or another method of contact at least every 3 months from the date of treatment discontinuation. All subsequent anti-cancer treatments are to be reported.

All patients are to be followed for 2 years or until death whichever comes first.

The assessments performed at these visits will include:

- [REDACTED]
- [REDACTED]
- [REDACTED]

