9.2. REPORTING OF ADVERSE EVENTS (AEs)

Report initiation for all AEs and SAEs will begin at the time of the first treatment visit and continue until the end of final study visit. All events will be followed to resolution or until the subject completes the study. A final assessment of outcome will be made at that time.

All AEs must be recorded in the subject's medical records and on the CRF. AEs will be reported using customary medical terminology along with the following information: the onset and end dates, whether the event is considered to be a SAE (see [Section 9.3](#)), the impact the event had on study treatment (see [Section 9.2.1](#)), the Common Terminology Criteria for Adverse Events (CTCAE) grade (intensity) of the event (see [Section 9.2.2](#)), the causality of the event (see [Section 9.2.3](#)), whether treatment was given as a result of the event (see [Section 9.2.4](#)), and the outcome of the event (see [Section 9.2.5](#)).

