9.2.1. Impact on Study Treatment

The impact the event had on the study treatment will be assessed as either: dose increased, dose not changed, dose rate reduced, dose reduced, drug interrupted, drug withdrawn, not applicable, or unknown. The "not applicable" assessment will be used only when the subject is no longer in the Treatment Phase of the protocol.

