[REDACTED]

[REDACTED]

Once the MTD has been determined, subjects enrolled in lower dose cohorts will be allowed to escalate the dose to the MTD, if acceptable per the Investigator's discretion. Subjects will be eligible for continuing treatment in absence of progressive disease or unacceptable toxicity or withdrawal of consent.

Part 2

In Part 2 of the study, patients will receive dovitinib in combination with the MTD of 2X-121 determined in Part 1. Part 2 will also follow a "3+3" design to determine the MTD of dovitinib when given in combination with 2X-121. The MTD is defined as one dose level (cohort) below the dose in which dose limiting toxicities (DLTs) were observed in $\geq 33\%$ of the participants.

The dose levels to be evaluated in Part 2 are shown below:

Dose Cohort	Combination 2X-121 and Dovitinib
Cohort 1	2X-121 (MTD) + 300 mg dovitinib
Cohort 2	2X-121 (MTD) + 400 mg dovitinib
Cohort 3	2X-121 (MTD) + 500 mg dovitinib

Dovitinib will be administered once daily (morning) on a 5 days on/2 days off schedule. In a 28 day cycle, dovitinib will be administered C1D1 - C1D5, C1D8 - C1D12, C1D15 - C1D19, and C1D22 - C1D26.

[REDACTED]

[REDACTED]

[REDACTED]

[REDACTED]

[REDACTED]

[REDACTED]

[REDACTED]

[REDACTED]

[REDACTED]

[figure not shown]
[REDACTED]

[REDACTED]

Once the MTD has been determined, subjects enrolled in lower dose cohorts will be allowed to escalate the dose to the MTD, if acceptable per the Investigator's discretion. Subjects will be eligible for continuing treatment in absence of progressive disease or unacceptable toxicity or withdrawal of consent.

An additional 3-6 patients will receive 2X-121 in combination with dovitinib once the MTD dose is determined.

A schematic of the "3 + 3" Dose Escalation Study Design is provided in Figure 2.1.

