2.2 Cohort/Treatment Groups

Subjects in Part 1 of the study are described below in Table 2-1.

Table 2-1 Treatment Groups

Dose Cohort	2X-121 Monotherapy Dose (BID)
Cohort 1	600 mg (morning dose: 200 mg + evening dose: 400 mg)
Cohort 2	800 mg (morning dose: 400 mg + evening dose: 400 mg)
Cohort 3	1000 mg (morning dose: 400 mg + evening dose: 600 mg)

Subjects in Part 2 of the study are described below in Table 2-2.

Table 2-2 Treatment Groups

Dose Cohort	Combination 2X-121 and Dovitinib
Cohort 1	2X-121 (MTD) + 300 mg dovitinib
Cohort 2	2X-121 (MTD) + 400 mg dovitinib
Cohort 3	2X-121 (MTD) + 500 mg dovitinib

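### SAP 8.3.1 gives treatment-emergent adverse events no end date, so events late in follow-up or on a later cancer therapy count as TEAEs

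*SAP*

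**What the plan says.** SAP Section 8.3.1 defines the term in one complete sentence: "TEAE are defined as adverse events with onset date on or after the first treatment". The next sentence gives the tabulation: "TEAEs will be summarized by treatment group, System Organ Class, and preferred term". The text after that is redacted. SAP Section 2.2 treats treatment groups and dose cohorts as the same thing (Tables 2-1 and 2-2).

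Protocol Section 9.2 sets the collection period. Reporting of adverse events and SAEs "will begin at the time of the first treatment visit and continue until the end of final study visit". Protocol Section 9.2.1 provides a not-applicable code for the effect on study treatment, and that "assessment will be used only when the subject is no longer in the Treatment Phase of the protocol", so events after treatment are foreseen. Protocol Section 4.4.2 states: "All patients are to be followed for 2 years or until death whichever comes first". The same section asks for all later anti-cancer treatments to be reported. The EOT visit falls 30 (±7) days after the last dose (Protocol Section 4.4.1), but neither document visibly uses it to end TEAE status.

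On dose changes, SAP Section 2.1.1 says that, after the MTD is determined, "subjects enrolled in lower dose cohorts will be allowed to escalate the dose to the MTD". This applies in both parts.

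**The concern.** A treatment-emergent window is meant to separate events that could plausibly be due to study drug from those of the disease and of later care. With no end, it cannot do so. In advanced solid tumours many subjects will progress, and some will start another therapy while still in follow-up. A toxicity of that next therapy meets the SAP definition.

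TEAE incidence and severity is a named safety outcome (SAP Section 2.6.5) that supports a secondary objective. Safety analysis is descriptive only (SAP Section 8.3), so the tables are the result and no model or test will absorb the extra events. Subjects who live longer also accrue more countable time, so cohorts can differ in TEAE incidence because of survival rather than dose.

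There is a smaller, related gap. If subjects move up to the MTD and tables are by treatment group, the reader needs to know which dose their later events are counted under.

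**Working it through.** **Inputs from the documents.** TEAE start: first treatment. TEAE end: none visible. Collection: to the final study visit. Follow-up: 2 years or until death, with the starting point of the 2 years not stated. EOT visit: 30 (±7) days after the last dose. DLT window: first 14 days (SAP Section 8.2.1.1). Maximum sample: 16 in Part 1 and 24 in Part 2 (SAP Section 3).

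**The plan's own figure.** The maxima follow from the 3+3 rules: Part 1, (1+3) + 6 + 6 = 16; Part 2, 3 × 6 + 6 = 24. Both agree with the SAP. The TEAE point does not depend on them.

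**Share of counting time after treatment.** Time on treatment and survival are not given, so both are assumed. Let m be months on treatment and f months followed after the last dose. The open window lasts m + f. The part more than one month (about 30 days) after the last dose is f − 1. The share is (f − 1)/(m + f).

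| m | f = 24 | f = 6 | f = 3 |
|---|---|---|---|
| 2 | 23/26 = 88% | 5/8 = 63% | 2/5 = 40% |
| 4 | 23/28 = 82% | 5/10 = 50% | 2/7 = 29% |
| 6 | 23/30 = 77% | 5/12 = 42% | 2/9 = 22% |

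If the 2 years run from first dose instead, a subject followed throughout has (24 − m − 1)/24: 21/24 = 88%, 19/24 = 79% and 17/24 = 71% for m = 2, 4 and 6.

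**Illustration in events.** Assume a constant background rate λ per month, unrelated to drug. The chance of at least one such event is 1 − exp(−λ(m + 1)) with a cut-off at one month after the last dose, and 1 − exp(−λ(m + f)) without one.

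| m, f | λ = 0.01: with cut-off → without | λ = 0.10: with cut-off → without |
|---|---|---|
| 2, 24 | 3% → 23% | 26% → 93% |
| 6, 24 | 7% → 26% | 50% → 95% |
| 6, 3 | 7% → 9% | 50% → 59% |

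The effect ranges from slight to dominant, and survival after treatment drives most of that range.

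**Escalated subjects.** At maximum cohort sizes, those enrolled below the MTD number 4 + 6 = 10 of 16 in Part 1 if Cohort 3 is the MTD, or 4 if Cohort 2 is. In Part 2 they number 6 + 6 = 12 of 24, or 6. Only those still on treatment when the MTD is set could escalate, so these are ceilings.

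**Effect on the primary outcome.** DLTs are counted over 14 days, and escalation is allowed only after the MTD is determined. Neither late events nor post-escalation events can enter the MTD decision of that part.

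**The case against.** The best defence has four parts.

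- **The data allow a repair.** All adverse events are listed by subject, with onset date, causality and effect on treatment recorded, for at most 40 subjects. A careful reader could pick out late events. This stands, but it leaves the summary tables as they are.
- **The long window may seldom be realised.** Follow-up ends at death, and entry requires a life expectancy of only 3 months. This stands, and is why the short follow-up columns are shown.
- **Capture in follow-up may be thin.** Follow-up visits are for survival status, may be by phone, and occur at least every 3 months. The list of assessments at those visits is redacted. Fewer events per month may be recorded than on treatment. This stands: the percentages are shares of time, not of events.
- **The sponsor may intend the EOT visit as the final visit for adverse events.** The protocol does not say so, and it calls the later contacts visits too. If that is the intent, the fix only writes it down.

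A reader might also infer more than the documents support. One inference is that events after escalation are charged to the starting dose. Treatment group does mean dose cohort, and enrolled cohort is a natural reading, but no visible text assigns an escalated subject's later events to any dose. The text after the tabulation sentence and the analysis populations (SAP Section 6) are redacted, so a rule may be there. A second inference is that by-cohort efficacy shares the fault. Only OS is visibly summarised by cohort; the visible PFS text gives listings, and the text after the ORR definition is redacted. Summarising OS by enrolled cohort is an ordinary choice.

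**Conclusion.** The point holds for the TEAE window. The definition is a complete, visible sentence without an end, and the protocol's collection and follow-up periods extend it well beyond treatment. Applied as written, it counts events of late disease and of later therapy as treatment-emergent and inflates the descriptive safety tables.

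The size rests on assumed treatment time and survival. The share of counting time more than 30 days after the last dose is 77% to 88% with 2 to 6 months of treatment and a full 24 months of follow-up after it. It is 22% to 50% with 4 to 6 months of treatment and 3 to 6 months of follow-up. The upper range should not be read as the proportion of events that are spurious.

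It would also be wrong to conclude that the MTD is at risk, because the 14-day DLT window and the order of escalation protect it. The handling of escalated subjects is a matter to confirm, not an established error.

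**What to change.** In SAP Section 8.3.1, end the TEAE window at the EOT visit (30 ±7 days after the last dose) or at the start of new anti-cancer therapy, whichever comes first. State which day applies if the EOT visit is missed. List later events separately, including any judged related to study treatment.

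Confirm in the same section that events after escalation to the MTD are tabulated by dose at onset, or shown as a separate post-escalation period. If the redacted text already says this, no change is needed.

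The cost is SAP wording and programming. Adverse event dates, treatment administration and later anti-cancer treatments are already to be collected. The small downside is that late related events leave the main table, so the separate listing should be reported alongside it.

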8.3.2 Clinical Laboratory Evaluations

All results of laboratory evaluations will be presented as by-subject listings.

[REDACTED]

[REDACTED]

[REDACTED]

[REDACTED]

[REDACTED]

[REDACTED]

[REDACTED]

[REDACTED]

[REDACTED]

[REDACTED]

[REDACTED]

[REDACTED]

8.3.3 Vital Signs

Vital sign assessments are performed in order to characterize basic body function. The parameters collected in this study are: systolic BP (mmHg), diastolic BP (mmHg), temperature ($^{\circ}\text{C}$), heart rate (bpm), respiratory rate (bpm). All vital sign results will be listed as by-subject listing.

[REDACTED]	
[REDACTED]	
[REDACTED]	
[REDACTED]	
[REDACTED]	
[REDACTED]	
[REDACTED]	
[REDACTED]	
[REDACTED]	
[REDACTED]	[REDACTED]
	[REDACTED]
	[REDACTED]
	[REDACTED]
	[REDACTED]
	[REDACTED]
	[REDACTED]
[REDACTED]	
[REDACTED]	[REDACTED]
	[REDACTED]
	[REDACTED]
	[REDACTED]
	[REDACTED]
	[REDACTED]
[REDACTED]	

All results of physical examination evaluations will be listed as by-subject listing.

[REDACTED]

[REDACTED] All ECG results will be listed as by-subject listing.

8.3.6 Serum Pregnancy Test

All the results for serum pregnancy test will be presented as a by-subject listing.

8.3.7 Urine Pregnancy Test

All data from Urine Pregnancy test will be presented as a by-subject listing.

8.3.8 Eastern Cooperative Oncology Group (ECOG) Test

All data from Eastern Cooperative Oncology Group (ECOG) test will be presented as a by-subject listing and/or summarized.

Bar Index	Approximate Length (%)
1	100
2	85
3	35
4	100
5	100
6	25
7	55
8	100
9	100
10	15

[REDACTED]

[REDACTED]

[REDACTED]

[REDACTED]

[REDACTED]

8.3.13 Pregnancy Notification

All data from Pregnancy Notification will be presented as a by-subject listing and/or summarized.

8.3.14 Pregnancy Outcome Report

All data from Pregnancy Outcome Report will be presented as a by-subject listing and/or summarized.

8.4 Analysis of Pharmacokinetic Outcome Measures

[REDACTED]

[REDACTED]

[REDACTED]

[REDACTED]

[REDACTED]

[REDACTED]

[REDACTED]

[REDACTED]

[REDACTED]

[REDACTED]

[REDACTED]

[REDACTED]

[REDACTED]

[REDACTED]

[REDACTED]

[REDACTED]

8.4.1 Estimate of Pharmacokinetic Parameters

The following PK parameters will be calculated using noncompartmental methods for each single dose administration in both parts of the study.

- Maximum observed plasma drug concentration (C_{\max})
- Apparent terminal elimination half-life ($t_{1/2}$)
- Time to maximum observed plasma drug concentration (T_{\max})
- Area under the plasma drug concentration-time curve (AUC) from time 0 to the time of the last quantifiable concentration (T_{last}) (AUC_{0-t})
- AUC from time 0 to infinity ($AUC_{0-\infty}$)
- Percentage of $AUC_{0-\infty}$ extrapolated from T_{last} to infinity (AUC_{ext})
- Apparent plasma clearance (CL/F)
- Apparent Volume of distribution (V_z/F)

9. APPENDIX 1

FIGURE 9-1: SCHEDULE OF ASSESSMENTS – PART 1

Study Phase	Screening Phase	Treatment Phase									Follow-up Phase	
		Treatment Cycle 1 (28 Days)				Treatment Cycle 2 (28 Days)			Subsequent Treatment Cycles (28 Days)			
Visit	SV	C1D1	C1D7	C1D15	C1D16	C2D1	C2D7	C2D15	CXD1	CXD15	EOT	FU
Window	Within 28 Days of C1D1		±1 Day	±1 Day	±1 Day	±1 Day	±1 Day	±1 Day	±1 Day	±1 Day	30 Days (±7) after last treatment dose	x (±3) Days after EOT
	X											
	X											
	X											
	X											
	X	X	X	X	X	X		X	X		X	
	X	X [5]	X [5]	X [5]	X [5]	X [5]	X [5]	X [5]	X [5]	X [5]	X [5]	
	X	X		X[6]		X[6]		X[6]	X[6]	X[6]	X	
	X	X				X			X		X	
	X	X				X			X		X	
		X										X
	X	X	X	X	X	X	X	X	X	X	X	X
		X	X	X	X	X	X	X	X	X	X	X
	X [8]								X [7]			
	X [8]								X [7]			
	X [8]								X [7]			
	X	X	X	X		X	X	X	X	X	X	
	X	X		X		X		X	X	X	X	
	X	X				X			X		X	
	X	X									X	
		X	X	X	X	X		X	X			

[illegible]

FIGURE 9-2: SCHEDULE OF ASSESSMENTS – PART 2

Study Phase	Screening Phase	Treatment Phase								Follow-Up Phase	
		Treatment Cycle 1 (28 Days)			Treatment Cycle 2 (28 Days)			Subsequent Treatment Cycles (28 Days)			
Visit	SV	C1D1	C1D7	C1D15	C2D1	C2D7	C2D15	CXD1	CXD15	EOT	FU
Window	Within 28 Days of C1D1		±1 Day	±1 Day	±1 Day	±1 Day	±1 Day	±1 Day	±1 Day	30 Days (±7) after last treatment dose	x (±3) Days after EOT
	X										
	X										
	X										
	X										
	X	X	X	X	X		X	X		X	
	X	X [5]	X [5]	X [5]	X [5]	X [5]	X [5]	X [5]	X [5]	X [5]	
	X	X		X[6]	X[6]		X[6]	X[6]	X[6]	X	
	X	X			X			X		X	
	X	X			X			X		X	
		X									X
	X	X	X	X	X	X	X	X	X	X	X
		X	X	X	X	X	X	X	X	X	X
	X [8]							X [7]			
	X [8]							X [7]			
	X [8]							X [7]			
	X	X	X	X	X	X	X	X	X	X	
	X	X		X	X		X	X	X	X	
	X	X			X			X		X	
	X	X								X	
		X	X	X	X		X	X			
	X										

			X		X	X		X	X	X			

[REDACTED]

10. APPENDIX 2

12. VERSION HISTORY

This is the first version of this document.
